Composite, dichotomous endpoint of all-cause mortality or unplanned hospital readmission assessed 90 days post index hospital discharge. Both inpatient and observation status hospitalizations will count towards the readmission outcome because either status represents an adverse event important to patients and healthcare systems. For the composite primary outcome, we will capture all patients with either date of death or eligible hospital readmission prior to 90 days post discharge as event-positive.

Secondary Outcome Variables

1. 90-day all-cause mortality
2. 90-day all-cause hospital readmission
3. 90-day all-cause emergency department visits
4. 90-day outpatient provider visits

5. 90-days cause-specific hospital readmissions for a) infection, b) chronic lung disease, c) heart failure, and d) acute kidney injury
6. 90-day acute care-free days alive, defined as the sum of days alive without inpatient, observation, and emergency department encounters during the 90 days after discharge
7. Percentage of patients with documented inpatient functional assessment or physical therapy consult
8. Percentage of patients with documented inpatient mental health assessment
9. Percentage of patients with documented referrals to a) rehabilitation services, b) speech therapy, and c) behavioral health
10. Percentage with outpatient follow-up within 7 days of hospital discharge
11. Percentage with designated medication reconciliation form in the electronic health record during the 90 days post hospital discharge
12. Percentage with palliative care consult
13. Percentage with completed care preferences documentation
14. Percentage discharged to hospice care from initial sepsis hospitalization
15. Place of death

Subject Selection

Consistent with our pragmatic study design concept, eligibility criteria are broad, the sample size is large, and study procedures are embedded into the context of routine care. Patients are eligible if they present to the emergency department and are subsequently admitted under inpatient or observation status to a participating hospital. Specific inclusion and exclusion criteria are described.

Inclusion Criteria:

1. At least 18 years of age upon admission
2. Oral/parenteral antibiotic or bacterial culture order within 24 hours of emergency department presentation
 - a) culture drawn first, antibiotics ordered within 48 hours or

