Detailed description of STAR services: At the initial contact with the patient or caregiver during hospitalization, the STAR navigator will introduce the STAR program and conduct health literacy screening and mental health screening using the Patient Health Questionnaire (PHQ)-2, with reflex administration of PHQ-9 for positive PHQ-2 (i.e., > or = 3).¹³⁰ The STAR navigator will convey results to the care team for appropriate behavioral health referrals. The STAR navigator will also confirm consultations with physical therapy (recommendations delivered to care team), antibiotic stewardship (i.e., a coordinated program that promotes appropriate antibiotic use) with additional infectious disease consult if ongoing Systemic Inflammatory Response Syndrome criteria more than 48 hours after infection onset (i.e., abnormal body temperature, heart rate, respiratory rate, white blood cell count), and palliative care team. For discharge, the STAR navigator will provide disease-specific education to the patient and caregiver and discharge education including what to expect during transition and a "playbook" with information on planned follow-ups. The navigator will also record all in-person and phone follow-up and all disciplines with post-acute touchpoints in the provider discharge plan. Because communication of care gaps and recommendations can be difficult in the complex acute care environment, our group has conducted a pilot with 15 patients to define communication strategies and contact points. Important elements include connecting to: patient and caregiver personal phones while

admitted; inpatient case managers for estimated discharge date, primary care provider information, and regular 24-48-hour contact until discharge; EHR-based messaging to providers; and post-acute care team within 24 hours of discharge (e.g., home health clinical supervisor) to initiate two-way communication.

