Irrespective of discharge location (e.g., home versus skilled nursing facility), the STAR navigator will provide monitoring through phone contact with patient, caregiver, or provider (as appropriate for post-acute care location) at <48 hours, 72-96 hours, and 7-10 days post-discharge. These touchpoints will include medication reconciliation, infection and respiratory symptom monitoring, vitals and weight checks, and confirmation that the patient can make scheduled outpatient appointments. Concerns identified through proactive monitoring will prompt a primary care provider contact for follow-up. If the primary care provider cannot be reached after one attempt, the navigator will contact the hospitalist back-up provider. Following the immediate post-acute interval, the STAR navigator will maintain weekly telehealth touchpoints with patients who remain at high-risk for poor outcome (i.e., any previous positive screen, high-risk comorbid condition [e.g., chronic lung disease, heart failure], or low health literacy) and every third week touchpoints with patients considered low-risk after the immediate post-acute interval. These 90-day post-acute touchpoints will include infection and respiratory symptom check, vitals and weight monitoring, and consideration for repeat outpatient provider visit. Identified concerns will prompt attempts to contact the primary care provider followed by hospitalist back-up provider. The STAR support service will complete 90 days post hospital discharge.

Statistical Analysis

Sample Size Determination: This study is designed to detect a 20% relative reduction in composite 90-day mortality and hospital readmission. The usual care group is indicated to have

roughly 40% combined 90-day mortality and readmission rate. With a total sample size of 4392 patients enrolled over 36 unit-months, we will have 90% power ($\alpha=0.05$) to detect a 20% relative reduction in composite 90-day mortality and hospital readmission.

Statistical Methods

Aim 1: Evaluate the effectiveness of an innovative, virtual nurse navigator implementation strategy to improve post-sepsis care.

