All primary and secondary analyses will follow intention to treat approach, such that all patients meeting identical criteria and randomized will be analyzed, regardless of adherence to intervention assignment. This real-world approach will assess intervention effectiveness while limiting selection biases associated with adherence. We will compare the two groups (STAR versus usual care) at baseline for age, sex, race, and comorbidities to assess for balance inferred randomization. The primary outcome is the composite of hospital readmission and mortality at 90 days post hospital discharge. Because hospitals are randomized to STAR in a staggered sequence and the outcome varies at the patient level, we will use a generalized linear mixed-effects model to compare the composite 90-day mortality and readmission primary outcome measure between the intervention conditions, adjusting for clustering effects across multiple levels (e.g., admitting hospital, implementation timing) to include hierarchical data structures. The intervention fixed-effect coefficient will compare STAR versus UC conditions (i.e., UC as reference). We will evaluate covariates for patient (e.g., sex, race, comorbidities, length of stay, discharge disposition [skilled nursing facility, rehabilitation, home]) and organizational factors (e.g., admitting hospital, guideline adherence, urban versus rural setting, implementation timing) to identify any potential differences between study arms. We will include covariates in model if unbalanced between STAR and UC groups. We will also evaluate effect

modification by conducting analyses stratified by these characteristics (e.g., discharge disposition) and by process measures with potential to effect outcomes (e.g., referrals).

Secondary outcomes are described below and will be assessed using the same approach. That is, we will construct generalized linear mixed-effects models, like for the primary outcome analysis, for individual assessments of secondary outcomes and process measures. We will test different distribution parameters to determine the optimal distribution family for each model and outcome variable (e.g., binomial, gamma distributions).

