9. Support service referrals. We will compare the receipt of support service referrals. Documented referrals to a) rehabilitation services, b) speech therapy, and c) behavioral health will each be captured separately from the electronic health record. We will construct separate generalized linear mixed-effects models with documented referral to rehabilitation services, speech therapy, and behavioral health each as the dependent variable of one model. Each variable will be assessed as a binary outcome at 90 days after hospital discharge. The intervention fixed-effect coefficient will compare STAR versus UC conditions, using an intent-to-treat approach.

10. Early outpatient provider follow-up. We will compare the receipt of early outpatient provider followup, defined as an outpatient provider encounter within 7 days of hospital discharge and captured from the electronic health record. We will construct generalized linear mixed-effects models with documented early outpatient provider follow-up as the dependent variable, assessed as a binary outcome at 7 days after hospital discharge. The intervention

fixed-effect coefficient will compare STAR versus UC conditions, using an intent-to-treat approach.

11. Outpatient medication reconciliation. We will compare the receipt of outpatient medication reconciliation, captured from the electronic health record. We will construct generalized linear mixed-effects models with designated outpatient medication reconciliation form completion as the dependent variable, assessed as a binary outcome at 90 days after hospital discharge. The intervention fixed-effect coefficient will compare STAR versus UC conditions, using an intent-to-treat approach.

12. Palliative care consult. We will compare the receipt of palliative care consult, captured from the electronic health record. We will construct generalized linear mixed-effects models with documented palliative care consult completion as the dependent variable, assessed as a binary outcome at index hospital discharge. The intervention fixed-effect coefficient will compare STAR versus UC conditions, using an intent-to-treat approach.

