experiences with the STAR program and perceived barriers and facilitators to act on STAR recommendations; and d) focused ethnography of the navigator role in the program conducted on four work days (two days for each navigator) at the three 8-month intervals during implementation. Focused ethnography is an innovative component of our study, selected to obtain a holistic and nuanced understanding of the navigator's role in the intervention. Interview recordings and ethnographic observation fieldnotes will be transcribed for coding and qualitative analysis using ATLAS.ti v8.0. We will perform content analysis using the constant comparison method, an inductive grounded theory approach for developing code structure through iterative comparison of newly coded text with previously coded text of the same theme until final thematic refinement is achieved. We will finalize the code list and repeat data review using the finalized code structure for coding reliability. Participant recruitment will be primarily facilitated through email survey invitation in REDCap. Subject identifiers, including email address, will also be tracked and captured in REDCap.

RECRUITMENT AND RETENTION PLAN

Recruitment Plan

Pragmatic Clinical Trial

Eligible patients at any of the (8) selected hospitals will be included in the study. Risk models will run each morning and automatically generate lists of eligible patients admitted over the prior 72 hours identified to be high-risk for readmission or mortality. During months allocated to the intervention, the navigator will receive the list of actively admitted, high risk patients via secure email. Assignment to a study arm will be based on the date the eligible patient is identified by the risk model. Patients will only be identified as eligible for randomization once during the index hospital stay, regardless of hospital length of stay. Patients with repeat hospitalization will be eligible for repeat study inclusion during admissions that begin more than

90 days after discharge from index hospitalization. Patients assigned to the intervention will be contacted by telephone via the bedside nurse (or other member of the care team) and introduced to the Sepsis Transition and Recovery program and navigation process prior to hospital discharge.

Mixed-methods process analyses

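### Effect modification is to be evaluated within strata of process measures such as referrals, which STAR influences after allocation, so a stratum can show a false STAR effect in either direction

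*Combined protocol and SAP*

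**What the plan says.** Five places in the combined protocol and SAP bear on this.

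- **Statistical Methods, Aim 1.** After listing patient and organisational covariates, the plan will evaluate effect modification in analyses stratified by those characteristics and "by process measures with potential to effect outcomes (e.g., referrals". Length of stay and discharge disposition are among the listed characteristics.
- **Recruitment Plan, Pragmatic Clinical Trial.** "Assignment to a study arm will be based on the date the eligible patient is identified by the risk model".
- **Study Procedures, Detailed description of STAR services.** After that date, and after mental health screening: "The STAR navigator will convey results to the care team for appropriate behavioral health referrals".
- **Secondary Outcome Variables, item 9.** "Percentage of patients with documented referrals to a) rehabilitation services, b) speech therapy, and c) behavioral health".
- **Statistical Methods, Aim 1, secondary outcome 9.** Each referral type gets its own STAR-versus-usual-care model: "Each variable will be assessed as a binary outcome at 90 days after hospital discharge".

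Nothing in the documents limits the effect-modification strata to variables fixed before allocation, gives a mediation or principal-stratum method, or labels the stratum results exploratory or non-randomised.

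**The concern.** The plan uses one variable in two roles: as a result of STAR (secondary outcome 9) and as a modifier of STAR's effect. The second role needs a variable that allocation cannot change.

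Suppose STAR leads to referral of patients whom usual care would not have referred. The referred STAR group then has a different prognostic mix from the referred usual-care group, and the same holds for those not referred. The difference in mix appears as a treatment effect.

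There may also be a timing problem. If the stratifier uses the 90-day definition of secondary outcome 9, its window coincides with that of death or readmission. A patient who dies early has less time to be referred, and a readmission may itself generate a referral, so the outcome would help to define the stratum.

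At stake is interpretation. A table of STAR effects by referral status invites the reader to conclude which patients, or which elements of care, benefit.

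**Working it through.** **Plan's own figures.** The documents give no referral rate and no link between referral and prognosis, so there is no stated figure to reproduce. The one anchor is Sample Size Determination: "roughly 40% combined 90-day mortality and readmission rate" under usual care, with a 20% relative reduction as the design effect. That is 40% to 32%, an odds ratio (OR) of (0.32/0.68)/(0.40/0.60) = 0.71.

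**Set-up (all inputs below are assumed).** Patients fall into three equal severity groups with mean risk 40%: either 25/40/55% or, for a weaker gradient, 32/40/48%. Each patient's risk is the same in both arms and referral does not change it, so the true OR is 1.00. STAR changes only the referral probability r in each group.

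**Formula.** Risk among the referred = Σ(r × risk)/Σr. Risk among the not referred = Σ((1−r) × risk)/Σ(1−r).

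**Case 1 in full.**
- Referred, usual care: (0.10×0.25 + 0.20×0.40 + 0.60×0.55)/0.90 = 0.435/0.90 = 48.3%.
- Referred, STAR: (0.20×0.25 + 0.60×0.40 + 0.90×0.55)/1.70 = 0.785/1.70 = 46.2%. OR 0.92.
- Not referred, usual care: (0.90×0.25 + 0.80×0.40 + 0.40×0.55)/2.10 = 0.765/2.10 = 36.4%.
- Not referred, STAR: (0.80×0.25 + 0.40×0.40 + 0.10×0.55)/1.30 = 0.415/1.30 = 31.9%. OR 0.82.

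**All cases** (usual care vs STAR; ORs are STAR relative to usual care):

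| Case | Risks % | Referral, usual care % | Referral, STAR % | Referred | Not referred |
|---|---|---|---|---|---|
| 1 | 25/40/55 | 10/20/60 | 20/60/90 | 48.3 vs 46.2, OR 0.92 | 36.4 vs 31.9, OR 0.82 |
| 2 | 25/40/55 | 10/20/60 | 60/70/90 | 48.3 vs 42.0, OR 0.78 | 36.4 vs 34.4, OR 0.91 |
| 3 | 32/40/48 | 10/20/60 | 20/60/90 | 44.4 vs 43.3, OR 0.95 | 38.1 vs 35.7, OR 0.90 |
| 4 | 32/40/48 | 10/20/60 | 60/70/90 | 44.4 vs 41.1, OR 0.87 | 38.1 vs 37.0, OR 0.95 |
| 5 | 25/40/55 | 10/20/30 | 20/40/60 | 45.0 vs 45.0, OR 1.00 | 38.8 vs 36.7, OR 0.92 |
| 6, usual care refers healthier patients | 25/40/55 | 60/40/20 | 80/70/60 | 35.0 vs 38.6, OR 1.17 | 43.3 vs 43.3, OR 1.00 |
| 7, referral unrelated to prognosis | 25/40/55 | 20/20/20 | 60/60/60 | OR 1.00 | OR 1.00 |
| 8, STAR does not change referral | 25/40/55 | 20/40/60 | 20/40/60 | OR 1.00 | OR 1.00 |

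**Extreme case.** Here referral follows severity perfectly. The sickest 20% have 60% risk, the next 40% have 40% and the remaining 40% have 30%, again 40% overall. Usual care refers the sickest 20% and STAR the sickest 60%.
- Referred: 60.0% vs (0.2×0.60 + 0.4×0.40)/0.6 = 46.7%, OR 0.58.
- Not referred: (0.4×0.40 + 0.4×0.30)/0.8 = 35.0% vs 30.0%, OR 0.80.

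**Simulation of case 1.** This used 400 stepped-wedge trials with eight hospitals, hospital log-odds SD 0.15 (assumed), and a logistic model with hospital and period fixed effects standing in for the planned mixed model. The unstratified analysis had median OR 1.00 and p<0.05 in 5.2% of trials. A false significant STAR benefit, for which 2.5% is the chance level, appeared in 22.8% of trials among the not referred (median OR 0.83) and in 7.7% among the referred (median OR 0.91). Milder inputs, including the weaker severity gradient, lowered these to 7.0% and 2.5%.

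**The case against.** **The sizes rest on assumptions.** This stands. The documents supply no referral rates or severity gradient, and bias requires both that STAR changes referral and that referral depends on prognosis. The first is what STAR intends. The second is plausible, because behavioural health referrals follow screening results. Neither is quantified.

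**STAR prompts referrals; it does not deliver them.** This also stands. The navigator passes on results and the care team refers, as it may under usual care. The STAR services description names behavioural health referrals and does not mention speech therapy. The argument needs only that STAR can influence the stratifier after allocation.

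**The plan is intention to treat:** "All primary and secondary analyses will follow intention to treat approach". That settles who is analysed and in which arm. It does not make a comparison within a post-allocation stratum a randomised one.

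**The 90-day window is stated for the outcome, not for the stratifier.** Fair. The timing problem is therefore conditional on the same definition being used.

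**The consequence is limited.** Largely right. This is one clause about a supplementary analysis. No decision rule depends on it, and implementation learning is assigned mainly to the Aim 3 mixed-methods work.

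A reader might also infer that the strata will favour STAR, or that the distortion matches the design effect. The documents support neither. Case 6 shows false harm. The moderate-case ORs of 0.78 to 0.95 are all weaker than the design OR of 0.71; only the extreme case, with perfect severity-ordered referral, passes it.

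**Conclusion.** The point holds as a flaw in a stated supplementary analysis. Stratifying the STAR comparison on referrals, or on other process measures that STAR influences after allocation, can produce stratum-specific effects when STAR has none.

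Neither size nor direction can be known in advance. Under the assumed inputs and a true null, ORs are about 0.78 to 0.95 in cases 1 to 4, 0.58 at the extreme and 1.17 in the reverse pattern. A stratum is unbiased when STAR leaves its severity mix unchanged, as in cases 7 and 8 and in one stratum each of cases 5 and 6. Because the direction is unknown, readers cannot correct for it.

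It would be wrong to infer that the main result is compromised. The primary intention-to-treat comparison does not condition on referral, and the sample size does not depend on it.

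**What to change.** In Statistical Methods, Aim 1:

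1. Delete process measures as stratification variables for effect modification.
2. Restrict effect modification to characteristics fixed when the patient appears on the risk-model list, for example age, sex, race, comorbidities, risk score, and urban or rural hospital. Test each as a STAR-by-characteristic interaction in the primary model.
3. Note that this rule also removes discharge disposition and length of stay, which are likewise determined after allocation.
4. Keep process measures as outcomes compared between arms, as already planned.
5. If their contribution to the effect is of interest, specify a separate mediation analysis, labelled exploratory and non-randomised, that handles the timing of referral relative to events: for example, referrals fixed by index discharge, or a landmark or time-varying approach. Simply counting referrals made before the first event is not enough, because patients with early events still have less time to be referred.

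The cost is SAP wording; the change to the strata needs no new data. The sponsor gives up a simple table of STAR effects by process measure received.

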1. All-cause mortality. We will assess the individual mortality component of the primary composite endpoint separately. We will construct generalized linear mixed-effects models with all-cause mortality as the dependent variable, assessed as a binary outcome at 90 days post discharge. The intervention fixed-effect coefficient will compare STAR versus UC conditions, using an intent-to-treat approach.

2. All-cause hospital readmission. We will assess the individual hospital readmission component of the primary composite endpoint separately. We will construct generalized linear mixed-effects models with all-cause hospital readmission, including inpatient and observation status, as the dependent variable, assessed as a binary outcome at 90 days post discharge. The intervention fixed-effect coefficient will compare STAR versus UC conditions, using an intent-to-treat approach.

3. All-cause emergency department visits. We will assess the number of emergency department visits. We will construct generalized linear mixed-effects models with the number of emergency departments visits as the dependent variable assessed at 90 days post discharge. We will use the Poisson distribution to model the outcome due to the expected distribution of the

counts of emergency department visits. The intervention fixed-effect coefficient will compare STAR versus UC conditions, using an intent-to-treat approach.

4. Outpatient provider visits. We will assess the number of outpatient provider office visits. We will construct generalized linear mixed-effects models with the number of outpatient provider office visits as the dependent variable assessed at 90 days post discharge. We will use the Poisson distribution to model the outcome due to the expected distribution of the counts of outpatient provider office visits. The intervention fixed-effect coefficient will compare STAR versus UC conditions, using an intent-to-treat approach.

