5. Cause-specific hospital readmission. We will assess the cause-specific hospital readmissions related to a) infection, b) chronic lung disease, c) heart failure, and d) acute kidney injury. We will construct separate generalized linear mixed-effects models for each of the four cause-specific hospital readmission conditions. The dependent variable for each model will be infection-, chronic lung disease-, heart failure-, and acute kidney injury-related hospital readmissions, respectively, assessed as a binary outcome at 90 days post discharge. The intervention fixed-effect coefficient will compare STAR versus UC conditions, using an intent-to-treat approach.

6. Acute care-free days alive. We will assess the total sum of days alive without inpatient, observation, and emergency department care utilization. The number of acute-care free days will be calculated from the date of index hospital admission through 90 days after discharge or date of death if prior to 90 days. We will construct generalized linear mixed-effects models testing different distribution patterns to determine the optimal distribution family for the count of acute care-free days. The intervention fixed-effect coefficient will compare STAR versus UC conditions, using an intent-to-treat approach.

7. Inpatient functional assessment or physical therapy consult. We will compare the receipt of inpatient functional assessment or physical therapy consult, captured from the electronic health record. We will construct generalized linear mixed-effects models with documented functional assessment or physical therapy consult as the dependent variable, assessed as a binary outcome at the time of hospital discharge. The intervention fixed-effect coefficient will compare STAR versus UC conditions, using an intent-to-treat approach.

8. Inpatient mental health assessment. We will compare the receipt of inpatient mental health assessment, captured from the electronic health record. We will construct generalized linear mixed-effects models with documented mental health assessment as the dependent variable, assessed as a binary outcome at the time of hospital discharge. The intervention fixed-effect coefficient will compare STAR versus UC conditions, using an intent-to-treat approach.

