13. Completed care preferences. We will compare the completion of care preferences documents, captured from the electronic health record. We will construct generalized linear mixed-effects models with care preferences document completion as the dependent variable, assessed as a binary outcome at index hospital discharge. The intervention fixed-effect coefficient will compare STAR versus UC conditions, using an intent-to-treat approach.

14. Discharged to hospice care. We will compare the discharged to hospice care from the index hospitalization for sepsis, captured from the electronic health record and hospital discharge records in the enterprise data warehouse. We will construct generalized linear mixed-effects models with discharged to hospice care as the dependent variable, assessed as a binary outcome at index hospital discharge. The intervention fixed-effect coefficient will compare STAR versus UC conditions, using an intent-to-treat approach.

15. Place of death. We will compare the place of death for individuals who die over the 90-day trial interval, captured from the electronic health record and hospital discharge records. We will construct generalized linear mixed-effects models with place of death as the dependent variable, assessed as a categorical outcome at 90 days after hospital discharge. The intervention fixed-effect coefficient will compare STAR versus UC conditions, using an intent-to-treat approach. In addition to primary intent-to-treat analyses, we will conduct modified intent-to-treat analyses excluding sepsis patients 1) who do not survive index hospitalization since STAR is designed to support patients during their transition out of the hospital; and 2) discharged against medical advice since providers do not have the opportunity to deliver full care and prepare the patient for discharge. Based on published data and internal estimates, we expect less than 10% of study patients will die during index hospitalization and fewer than 2% will be discharged against medical advice. We will present results from group comparisons as odds ratios and 95% confidence intervals.

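### Visit counts (secondary outcomes 3 and 4): Poisson is named without a dispersion term, the family is elsewhere left open without a selection rule, and odds ratios do not fit a log-link count model

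*Combined protocol and SAP*

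**What the plan says.** All references are to the combined protocol and SAP, Statistical Methods, Aim 1.

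- **Family for the counts.** Under secondary outcome 4: "We will use the Poisson distribution to model the outcome due to the expected distribution of the counts of outpatient provider office visits". Secondary outcome 3 (emergency department visits) has a parallel sentence. Neither mentions a scale parameter, a patient-level random effect, a robust variance or a fallback model.
- **Family in general.** The paragraph introducing the secondary outcomes says: "We will test different distribution parameters to determine the optimal distribution family for each model and outcome variable". It gives no criterion and no time for the decision. The open search is repeated for one outcome only, outcome 6: "testing different distribution patterns to determine the optimal distribution family for the count of acute care-free days".
- **Clustering.** The mixed model is described as "adjusting for clustering effects across multiple levels (e.g., admitting hospital, implementation timing". These levels are examples; no patient-level effect is among them.
- **Analysis set.** The intention-to-treat rule is that "all patients meeting identical criteria and randomized will be analyzed, regardless of adherence to intervention assignment". After outcome 15 the plan adds: "we will conduct modified intent-to-treat analyses excluding sepsis patients 1) who do not survive index hospitalization". It also says "we expect less than 10% of study patients will die during index hospitalization". These deaths therefore stay in the main analysis, and outcomes 3 and 4 do not say what visit count they receive.
- **Effect measure.** The same paragraph ends: "We will present results from group comparisons as odds ratios and 95% confidence intervals". No exception is made for counts.

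**The concern.** A Poisson model fixes the variance at the mean. If patients differ in their underlying visit rate, the variance exceeds the mean, the model standard error is too small, and a chance difference in visits is called significant more often than the nominal 5%.

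The plan does not settle whether this can happen. If the sentences under outcomes 3 and 4 govern, Poisson is final and nothing protects the standard error. If the general sentence governs, another family may be chosen, but with no rule for choosing it.

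The effect measure is a separate matter that does not depend on dispersion. An exponentiated coefficient from a log-link count model is a ratio of mean counts, so calling it an odds ratio would mislabel the result.

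**Working it through.** **Inputs from the plan.** Eight hospitals, one crossing over every four months (Randomization); 4392 patients over 36 months (Sample Size Determination; Length of Active Enrollment); two-sided tests at 0.05; in-hospital deaths below 10%. The plan states no figure for the visit counts, so there is none to reproduce. Its 90% power claim concerns the primary composite; only the total of 4392 is used here, to set the design.

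**Inputs assumed.** Variance/mean 1 to 3; survivor mean 1 to 5 visits; hospital standard deviation 0.15 on the log scale; equal hospital-period sizes; log link. With 36/4 = 9 periods there are 8 × 9 = 72 hospital-periods, and 4392/72 = 61 patients in each.

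**1. Hospital intercept and period effects only.** If variance/mean = φ, the Poisson standard error is too small by √φ, and the true error of a nominal 5% test is 2Φ(−1.96/√φ). The simulation used a null effect, mean 1, a Laplace Poisson mixed model with a Wald z test, and 10,000 trials per setting (Monte Carlo SE 0.2 to 0.4 points).

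| φ | Formula | Simulated, Poisson | Simulated, scaled by Pearson dispersion |
|---|---|---|---|
| 1 | 5.0% | 6.2% | 6.2% |
| 1.5 | 11.0% | 11.8% | 5.8% |
| 2 | 16.6% | 16.9% | 5.1% |
| 3 | 25.8% | 26.1% | 5.3% |

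The 6.2% at φ = 1 reflects having only eight hospitals; with hospitals as fixed effects it was 4.9%. Scaling does not cure this excess: at φ = 1 and hospital standard deviation 0.05, both fits gave about 7.5%. At φ = 2 the Poisson rate depends little on the hospital standard deviation (16.2% at 0.05, 16.8% at 0.30).

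**2. In-hospital deaths scored as zero.** Suppose a fraction p die in hospital and are given zero visits, and survivors are exactly Poisson with mean m. The overall mean is (1−p)m and the variance is (1−p)m + p(1−p)m², so variance/mean = 1 + pm. At the ceiling p = 0.10:

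- m = 1: ratio 1.1; error 6.2% by formula, 7.0% simulated
- m = 3: ratio 1.3; 8.6% and 9.3%
- m = 5: ratio 1.5; 11.0% and 11.3%

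At p = 0.05 the formula gives 5.6%, 6.8% and 8.0% (simulated 6.3%, 7.3%, 8.2%).

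**3. Hospital-by-period random effect added.** Treatment is constant within a hospital-period, so this effect picks up most of the excess variance of the hospital-period means. Results from a linearised mixed model at mean 1, 1200 trials on common data (Monte Carlo SE about 0.7 points):

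| Fit | φ = 1.5 | φ = 2 | φ = 3 |
|---|---|---|---|
| Unscaled, maximum likelihood | 7.2% | 7.9% | 7.5% |
| Unscaled, restricted likelihood | 5.8% | 5.9% | 5.3% |
| Joint scale, maximum likelihood | 5.4% | 6.0% | 5.7% |
| Joint scale, restricted likelihood | 4.7% | 4.9% | 4.5% |

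A separate run of 700 trials per setting (Monte Carlo SE about 0.9 points) gave 6.7% to 9.1% unscaled by maximum likelihood and 5.0% to 7.4% by restricted likelihood. Multiplying the standard error by the dispersion after such a fit counts the excess variance twice: in 2000 trials the error fell to 4.1%, 2.0% and 0.6% at φ = 1.5, 2 and 3.

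**4. Effect measure.** With a log link, log(mean) = … + β × STAR, so exp(β) = mean under STAR divided by mean under usual care. This is a rate (mean) ratio.

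**The case against.** The strongest reply is that the plan cannot be faulted on both readings at once. If Poisson is fixed, there is no open search; if the search governs, overdispersion can be dealt with before results are reported, and testing distribution parameters could even cover a scale parameter. This stands in part: the harm in step 1 arises only on the first reading. But the second supplies no rule, so neither reading is adequate as written.

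A reader might infer that these tests will run at 26% error. The documents do not support that: every variance/mean ratio above is assumed, and the clustering wording permits a hospital-by-period effect that removes most of the inflation. Nor can what remains after adding that effect be attributed simply to the missing dispersion term. It depends on the estimator and on having few hospitals, and unscaled restricted likelihood is already near nominal.

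A reader might also infer that in-hospital deaths will be scored as zero. The plan does not say so, 10% is a ceiling, and the modified analysis leaves these patients out. At a survivor mean of 1, the simulated 7.0% barely exceeds the 6.2% seen with no overdispersion.

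Finally, the odds-ratio sentence closes a paragraph on place of death and the modified analyses, and 12 of the 15 secondary outcomes are binary or categorical. It may have been meant for those. As worded, it covers every group comparison.

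**Conclusion.** The point holds in conditional form and is minor. Certain from the text: Poisson is named without a dispersion term, the general sentence leaves the family open without a rule, the scoring of in-hospital deaths is unstated, and the odds-ratio sentence does not fit a count model. The mislabelling assumes the usual log link, which the plan does not state.

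The size of any error inflation is not established. It ranges from almost none to about 26%, depending on an assumed variance/mean ratio of up to 3, on whether a hospital-by-period effect is fitted, and on the estimator. Two of fifteen secondary outcomes are affected, plus the effect label for acute care-free days if a log-link family is chosen. Nothing here bears on the primary analysis or the sample size.

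**What to change.** - For outcomes 3 and 4, replace the open family search with one pre-specified overdispersion-robust count model, and say that it overrides the general sentence. An example is a Poisson mixed model with log link and an estimated patient-level scale. A negative binomial model or a patient-level random effect would serve the same purpose.
- If a hospital-by-period random effect is included, estimate the scale jointly with the variance components; do not multiply the standard errors afterwards. Name the estimator.
- State how patients who die in hospital are counted.
- Report rate (mean) ratios with 95% confidence intervals for outcomes 3 and 4. Keep odds ratios for binary or categorical outcomes, and for outcome 6 use the measure that matches the chosen family.

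**Cost.** SAP wording and one model statement, with no new data. With a hospital intercept only, intervals widen by √φ − 1: 22%, 41% and 73% at φ = 1.5, 2 and 3. With a hospital-by-period effect they are about 5% to 7% wider when maximum-likelihood fits are compared, or about 10% to 11% wider for restricted-likelihood joint scale against unscaled maximum likelihood. Without overdispersion, and with the same estimator, they are essentially unchanged. The small excess from having eight hospitals remains in any case.
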